2 INTRODUCTION

2.1 STUDY RATIONALE

Despite the worldwide acknowledgment of exercise as a beneficial, non-pharmacological therapy for patients with heart failure (HF), many patients, particularly those with heart failure with preserved ejection fraction (HFpEF), do not engage in regular exercise and are unable to sustain exercise once started in a program. Patients with HFpEF report difficulties finding a routine place to exercise that includes support and accountability delivered near their home as barriers to continued exercise. These challenges are exacerbated by the ongoing COVID-19 pandemic. Therefore, we propose HEART Camp Connect that builds on the previously efficacious HEART Camp intervention. The primary objective of this study is to establish the feasibility and preliminary efficacy of the HEART Camp Connect intervention in patients with heart failure with preserved ejection fraction. We will accomplish this objective with two aims. Aim 1 examines the feasibility of administering HEART Camp Connect to patients with HFpEF. Our feasibility assessment will focus on process (e.g. recruitment rates, retention), resources (e.g. physical capacity, staff availability), management (e.g. data capture and management), and science (e.g. testing psychometrics of tools in the HFpEF population). Aim 2 tests the preliminary effects of HEART Camp Connect compared to enhanced usual care on adherence to exercise, physical activity, function, inflammation, patient-reported outcomes, and our theory-based interventional components. Impact: Exercise benefits patients with HFpEF by reducing morbidity and mortality and improving symptoms and quality of life. The proposed study uses a technology facilitated, theory-based intervention to help patients with HFpEF start and continue an exercise program over time. This feasibility, pilot study will give us data to refine the intervention and allow us to gather preliminary data for a competitive application to a federal funder.

2.2 BACKGROUND

Heart failure with preserved ejection fraction (HFpEF) is a growing public health concern. Over 13 million adults in the world, including 3 million in the U.S., live with severe activity intolerance and poor quality of life associated with HFpEF.^{1,2} HFpEF is difficult to manage, is quickly surpassing reduced ejection HF as one of the most common causes of hospitalization in the U.S., and is a significant driver of the \$30.7 billion annual cost of HF.¹ In the last decade, improvements have been made in the treatment of reduced ejection fraction HF and pharmacological therapies are standardized for these patients.³ However, these same therapies tested in HFpEF do not show significant benefits.⁴ SGLT2 inhibitors, initially developed to treat diabetes, have shown promise in recently completed clinical trials, but remain off-label for adults with HFpEF.^{5,6} Non-pharmacological interventions, such as exercise, show promise in improving physiologic and patient-reported outcomes, but require adherence to behavioral change, which remains a barrier to achieving improved health outcomes.⁷⁻⁹ This study tests the feasibility, acceptability, and preliminary effects of an intervention designed to promote exercise adherence in adults with HFpEF.

Exercise is a promising, non-pharmacological strategy to improve outcomes in adults with HFpEF.¹⁰ Outcomes from exercise trials in HF are encouraging, with studies demonstrating exercise as safe and eliciting improved aerobic capacity (peak VO₂) and quality of life.¹¹⁻¹⁵ However, key gaps in this evidence remain. 1. Most studies to date have enrolled adults with HF (HFpEF and HFrEF), including our group's HEART Camp study,¹⁶ instead of focusing exclusively on HFpEF. 2. HFpEF trials have inconsistently defined

HFpEF with ejection fractions ranging from 40 to 50% and above. The validated H2FPEF algorithm¹⁷ is now available to identify HFpEF which we incorporate into our inclusion/exclusion criteria. 3. Prior exercise interventions tested in HF were not specifically designed to promote adherence using theory-based components. HEART Camp Connect is designed to promote adherence to exercise by supporting the adoption and maintenance of exercise behavior. 4. Adherence is inconsistently defined across studies and often not objectively measured. Several studies use session attendance as a measure of adherence, but this does not allow for examination of dose-response effects or comparison to other clinically meaningful outcomes.¹⁸⁻²⁰

In this study, we monitor coaching session attendance and measure adherence objectively using minutes of moderate intensity exercise from a heart rate monitor. 5. No studies have tested interventional effects on inflammatory biomarkers, despite the known relationship between HFpEF and inflammation.²¹ This pilot incorporates examination of the impact of exercise on inflammatory biomarkers. 6. Cardiac rehabilitation is the predominate model for exercise in adults with HF, but the program is not specifically designed for adults with HFpEF and current Medicare guidelines do not reimburse attendance.²² Further, exercise is rarely sustained after program completion and programs are often inaccessible. This has resulted in notoriously low attendance at cardiac rehabilitation and subsequent poor long-term adherence to exercise.²³⁻²⁷ Our intervention is delivered virtually making exercise content accessible to participants at any time to improve sustainability.

Adherence is the Achilles heel of exercise in HF. The 2013 ACCF/AHA Guideline for the Management of Heart Failure recommends exercise as a non-pharmacological therapy that is safe and effective for individuals with HF (Class I - Level of Evidence A).¹⁰ Yet, studies indicate that as many as 91% of patients with HF do not participate in regular exercise.²⁸⁻³⁰ Therefore, promoting adherence to exercise in HF, particularly HFpEF, is a major priority for the National Heart Lung and Blood Institute (NHLBI) and the long-term goal of this proposal.³¹

HFpEF and exercise in HFpEF are assigned a high priority status by the NHLBI. The NHLBI convened two working groups, one addressed exercise as a non-pharmacological treatment for HF (2015)⁷ and the other (2019)³¹ identified knowledge gaps and set priorities for HFpEF research in the next 10 years. The HFpEF working group urged the development of effective HFpEF treatment strategies and referred to HFpEF as the greatest unmet need in cardiovascular medicine today. The panels set several priority targets for future study, including: 1. to examine optimal strategies and interventions to promote exercise initiation and adherence; 2. to identify behavioral mechanisms to improve adherence to exercise in HF; and 3. examine longitudinal changes in inflammatory biomarkers to better understand correlates to clinical status in HFpEF.^{7,31} This proposal addresses these high priority areas by evaluating the feasibility, acceptability and preliminary efficacy of HEART Camp Connect in promoting adherence to exercise, and physical activity and function, inflammatory markers, patient-reported outcomes, and theory-based components in HFpEF.

2.3 RISK/BENEFIT ASSESSMENT

2.3.1 KNOWN POTENTIAL RISKS

The risks associated with this study include those associated with cardiopulmonary exercise testing, venipuncture, exercise, emotional or psychological discomfort while answering questionnaires, and the risk of loss of confidentiality.

Cardiopulmonary exercise testing (CPET):

CPET has been shown to be safe in adults with high-risk cardiovascular diseases including heart failure. (Skalski 2012). However, participants may experience shortness of breath, angina, cardiac arrhythmias, or bronchospasm during CPET. All CPET will be completed in the pulmonary function lab at Nebraska Medicine - Durham Outpatient Center or Oakview Clinic under the supervision of a physician or advanced practice provider that has been trained in advanced cardiac life support (ACLS). Participants will walk on a treadmill or pedal a stationary bike for the test.

Blood draws:

Participants are at risk for pain, discomfort or infection at the venipuncture site.

Exercise: Exercise training may have an associated risk of cardiac arrhythmias, blood pressure disturbances, fatigue, muscle, and joint discomfort, and ultimately death. Exercise training in stable chronic HF patients has been shown to be safe in clinical trials and became part of the recommended Heart Failure Society of America guideline of evidence-based care in 2010.

Emotional/Psychological Discomfort:

Participants may experience fatigue, emotional or psychological discomfort when completing study questionnaires.

Loss of Confidentiality:

There is a risk of a loss of participant confidentiality. We have taken measures as outlined above to minimize this risk to the greatest extent possible. Although reasonable efforts have been taken, confidentiality cannot be guaranteed since research data will be transmitted electronically to REDCap.

2.3.2 KNOWN POTENTIAL BENEFITS

Participants may benefit from exercise although benefits are not guaranteed.

2.3.3 ASSESSMENT OF POTENTIAL RISKS AND BENEFITS

Minimization of Risk of CPET:

Risk of CPET is minimized with testing completed under the supervision of a physician or advanced practice provider trained to recognize adverse events and in initiating an ACLS protocol. Safeguards are in place to protect patients before and during testing. At both testing sites, prior to beginning the test, a technician will measure vital signs - including heart rate and blood pressure - to ensure normal pre-test values. Abnormal values will result in the test being rescheduled. During testing, the technician will stand within 2 feet of the patient at all times to "spot" them in case of an adverse event. All patients wear a gait belt during testing to support the patient if needed during an emergency. The treadmill is

equipped with an emergency stop button that can be pushed if needed during the test. A second stop button is attached to a wristband worn by the patient that would be pulled if the patient were to fall or stumble. The bike is powered by the patient so if the patient is in distress and stops pedaling, the bike stops. Patients are monitored throughout the testing with an EKG and frequent blood pressure readings. We will follow Nebraska Medicine policy in the event of an adverse event during testing. If the patient were to suffer a cardiac arrest during testing, the code cart is readily available and ACLS would be initiated by the supervising provider. Security would be notified and the hospital-based code team would be alerted to respond. If testing is completed at the Oakview clinic, security would notify the rapid response team who would respond.

Minimization of Risk of Blood Draws:

To mitigate the risk of infection or discomfort at the venipuncture site, we will attempt to coordinate study-related venipuncture with that needed for clinical care as much as possible. In addition, blood will be collected at an outpatient laboratory center at Nebraska Medicine by a certified phlebotomist.

Minimization of Risk of Psychological Discomfort:

We advise all participants that they are under no obligation to respond to our questions and may decline to answer or stop at any time. Should a participant experience fatigue, we will allow them to take a break and continue or schedule another time within the next 48 hours to complete remaining questionnaires. If a subject responds to the symptom questionnaires that they have often or always felt depressed and/or hopeless in the past 7 days the researchers will refer them to their Primary Care Provider and provide a list of mental health resources including the Boys Town Grief Hotline. If upon questioning as to whether they have any plans to hurt themselves, they respond with a "yes" they will be immediately escorted to the Emergency Department or 9-1-1 will be contacted on their behalf.

Minimization of Risk of Exercise:

All participants will have successfully completed a cardiopulmonary exercise test (CPET). The results from the CPET will be used to develop an individualized exercise prescription for each participant that will guide heart rate parameters during exercise. Participants will be taught to monitor the intensity of their exercise by using heart rate and the rating of perceived exertion from their participation in our study orientation. We reduce the risk of exercising at home by requiring that another adult be present during the exercise in the event a subject experiences an adverse event requiring medical attention. The other adult will be instructed to contact the provider if the participant experiences a non-emergent adverse event or initiate local EMS, in the event of an emergency. The other adult will be instructed to then follow the instructions of the dispatcher. A list of potential adverse events that would warrant a call to a provider or EMS was attached to the application and will be shared with all participants. It is important to note that 150 minutes of moderate-intensity exercise is recommended for these patients and HFrEF patients are not eligible for cardiac rehabilitation. If these patients were not participating in this study, they could be doing this exercise on their own without the guidance that results from participating in this study.

Minimization of Risk of Loss of Confidentiality:

To protect against possible risks to confidentiality, research data will be stored in a locked

cabinet in the research office of the PI. Subjects' names and other contact information (phone and emails if available) will be kept in a locked file accessible only by the PI. The contact information is needed in order to schedule study-related activities. All records will be coded with study identification numbers and kept in locked files in a locked research office. All downloaded files from the server will be kept on the hard drive of the principal investigator's computer, which is password-protected, and housed in PI's research office. All study personnel will be CITI trained. Study personnel will be involved in meetings and training sessions regarding data collection procedures in which procedures to ensure confidentiality will be covered.

3 OBJECTIVES AND ENDPOINTS

OBJECTIVES	ENDPOINTS	JUSTIFICATION FOR ENDPOINTS
Primary		
Assessment of Feasibility & Acceptability	Process, resources, procedures, data management, fidelity, acceptability	Needed to refine intervention for future testing
Secondary		
Preliminary effects on exercise	Minutes of exercise/week	We are not statistically powered to test for an effect
Tertiary/Exploratory		
Preliminary effects on symptoms & interventional strategies	Symptoms, quality of life, interventional mechanisms	Evaluate symptoms and intervention strategies

4 STUDY DESIGN

4.1 OVERALL DESIGN

Single-site feasibility randomized controlled trial/pilot study

4.2 SCIENTIFIC RATIONALE FOR STUDY DESIGN

We need to test our planned strategies to support a larger trial.

4.3 JUSTIFICATION FOR INTERVENTION

Adults with heart failure are recommended exercise as part of their plan of care; however, few do and in large part because they do not know how to get started. Our study helps to initiate exercise and sustain it over time.

4.4 END-OF-STUDY DEFINITION

The end of the study is defined as completion of the 24 week follow-up assessment shown in the Schedule of Activities (SoA), **Section 1.3**.

5 STUDY POPULATION

5.1 INCLUSION CRITERIA

1. *Diagnosis of heart failure with an ejection fraction greater than or equal to 50*
2. *Age greater than or equal to 19 years old*
3. *English-speaking*
4. *Echocardiogram in prior 24 months*
5. *Stable pharmacologic therapy in past 30 days*
6. *Score greater than or equal to 6 on the H2FPEF algorithm or hemodynamic evidence of HFpEF (i.e., elevated pulmonary wedge pressure)*

5.2 EXCLUSION CRITERIA

1. Life-limiting illness precluding study completion
2. Clinical evidence of decompensated heart failure
3. Unstable angina or marked shortness of breath on exertion at less than 2 metabolic equivalents
4. Myocardial infarction, coronary artery bypass graft, or biventricular pacemaker in prior 6 weeks
5. Orthopedic or neuromuscular disorders preventing aerobic exercise
6. Cardiopulmonary exercise test results that preclude safe exercise
7. Unwilling/unable to complete pre-randomization procedures
8. Pregnancy
9. Implantable cardioverter defibrillator

5.3 LIFESTYLE CONSIDERATIONS

N/A

5.4 SCREEN FAILURES

Screen failures are defined as participants who consent to participate in this study but are not subsequently assigned to the study intervention or entered in the study. Individuals who do not meet the criteria for participation in this trial (screen failure) because of meeting one or more exclusion criteria that are likely to change over time may be rescreened. Examples include the successful treatment of a previous affective disorder, and the lifting of physical activity restrictions previously in place. Rescreened participants will be assigned the same participant number as for the initial screening.

5.5 STRATEGIES FOR RECRUITMENT AND RETENTION

Study personnel will coordinate all recruitment and enrollment from Nebraska Medicine (NM). Inclusion/exclusion criteria are listed above. Potential participants will be approached in our HFpEF Optimize Clinic or in the Home Instead Center for Successful Aging Gerontology clinics. As a secondary recruitment strategy, we will use the UNMC/NM Opt-in database. Informed consent will be completed using the UNMC RSS e-consent portal or in-person on paper depending on the participant's preference by study personnel. More detail about screening, recruitment, and consent is provided in subsequent sections.

6 STUDY INTERVENTION(S) OR EXPERIMENTAL MANIPULATION(S)

6.1 STUDY INTERVENTION

No text is to be entered in this section; rather it should be included under the relevant subheadings below.

6.1.1 STUDY INTERVENTION

The HEART Camp Connect intervention is founded in social-cognitive theory⁴⁶ and the future-oriented motivation and self-regulation model proposed by Miller and Brickman.⁴⁷ HEART Camp Connect (n=25) includes weekly virtual coaching sessions with experienced coaches from Engage. For 3 weeks per month, coaches and participants meet 1-on-1 via videoconference to review heart rate data, exercise diaries from the prior week and initiate discussion related to behavioral change mechanisms. One week per month HEART Camp Connect participants will be assigned to a small group (1 coach:5 participants) exercise/observation session. During these sessions, coaches will demonstrate exercises and observe participants via videoconference for proper form and real-time encouragement in a group setting. Coaches will call any HEART Camp Connect participant that fails to

attend their scheduled weekly coaching session for 2 consecutive weeks. Participants achieving a minimum of 120 minutes of moderate-intensity exercise per week on average weeks 1-12 will be given the option to opt-out of coaching sessions for weeks 13-16. We recognize that this could potentially create variation in the dose of the coaching and therefore, will closely monitor the minutes of coaching per participant throughout the study. We will also closely monitor adherence during this time. Participants that relapse (become non-adherent for 2 consecutive weeks) for any reason (e.g., hospitalization, loss of motivation) will return to weekly coaching for the remainder of the intervention. Testing optional coaching is part of our feasibility assessment and increases the future scalability of this intervention. In the sustainability period (Weeks 17-24), weekly coaching stops, and HEART Camp Connect participants are expected to self-regulate exercise and maintain adherence.

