1.1 SYNOPSIS

Title:	HEART Camp Connect: A Feasibility Study
Grant Number:	NA
Study Description:	The proposed study uses a technology-facilitated, theory-based intervention to help patients with HFpEF start and continue an exercise program over time. This feasibility, pilot study will give us data to refine the intervention and allow us to gather preliminary data for a competitive application to a federal funder.
Objectives:	Our overall objectives for this study are to: (1) evaluate the feasibility of a virtual, theory based exercise training and coaching intervention in adults with HFpEF; and (2) examine the preliminary effects of this intervention on adherence to exercise, physical function, key inflammatory markers, and patient-reported outcomes.
Endpoints:	Primary Endpoint: 3 months Secondary Endpoints: 6 months
Study Population:	We will enroll 25 participants with heart failure with preserved ejection fraction 19 years of age or older from Nebraska Medicine in Omaha, Nebraska.
Phase:	Feasibility
Description of Sites/Facilities Enrolling Participants:	Single site study, recruiting in the U.S. only at Nebraska Medicine in Omaha, Nebraska
Description of Study Intervention/Experimental Manipulation:	Participants are randomized to enhanced usual care or a 3 month coaching intervention.
Study Duration:	24 months
Participant Duration:	6 months

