6.3 MEASURES TO MINIMIZE BIAS: RANDOMIZATION AND BLINDING

Participants are randomized to intervention or usual care using a random number generator in a 1:1 intervention to control fashion. Due to funding restraints we are not using blinded data collectors for this pilot feasibility study.

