7.1 DISCONTINUATION OF STUDY INTERVENTION/EXPERIMENTAL MANIPULATION

If patients are unable to safely complete the CPET or if their CPET results indicate they exceed our thresholds for cardiorespiratory fitness, they will be immediately withdrawn from the study. If the patient withdraws consent, the patient will be removed from the research study..

When a subject discontinues from HEART Camp Connect but not from the study, remaining study procedures will be completed as indicated by the study protocol. If a clinically significant finding is identified (including, but not limited to changes from baseline) after enrollment, the investigator or qualified designee will determine if any change in participant management is needed. Any new clinically relevant finding will be reported as an adverse event (AE).

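### Section 6.1.1 attaches n=25 to HEART Camp Connect, in context the coached arm, while the synopsis enrols 25 in total and Section 6.3 randomises 1:1; read as an arm size, the figure contradicts the total

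*Combined protocol and SAP*

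**What the plan says.** Three current statements in the protocol bear on the planned size.

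- Section 1.1 (Synopsis, Study Population): "We will enroll 25 participants with heart failure with preserved ejection fraction 19 years of age or older". The same table describes two arms, enhanced usual care and coaching.
- Section 6.3: "Participants are randomized to intervention or usual care using a random number generator in a 1:1 intervention to control fashion".
- Section 6.1.1: "HEART Camp Connect (n=25) includes weekly virtual coaching sessions with experienced coaches from Engage".

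Section 9.2 (Sample Size Determination) gives no number. It says only that the size reflects expected recruitment and not a power calculation. I found no control-arm size and no total other than 25 anywhere in the text.

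**The concern.** A reader who takes the three statements at face value cannot tell how many people the trial plans to randomise, or how many it plans to coach. If 25 is the total, recruiting 25 people completes the trial. If 25 is the coached arm, it is about half of what is needed.

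This matters more here than a stray number usually would, because feasibility and acceptability are the primary endpoint (Sections 3 and 9.1). Recruitment, coach availability and staff availability are among the things being assessed (Sections 1.3 and 2.1). The planned size is the yardstick for recruitment, and the coached-arm size is the denominator for anything described among coached participants only.

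**Working it through.** **What HEART Camp Connect denotes in Section 6.1.1.** The name is also in the study's title, so this has to be settled first. The sentence carrying n=25 lists what the intervention contains. Later in the section the same label marks the people who are coached: "One week per month HEART Camp Connect participants will be assigned to a small group (1 coach:5 participants) exercise/observation session". Section 2.1 (Aim 2) sets HEART Camp Connect against enhanced usual care. Section 7.1 separates leaving it from leaving the trial: "When a subject discontinues from HEART Camp Connect but not from the study". On its natural reading, then, n=25 is the size of the coached arm.

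**Inputs.** Total N = 25 (Section 1.1); two arms (Section 1.1); allocation 1:1, so a fraction of 1/2 to coaching (Section 6.3); coached-arm n = 25 (Section 6.1.1).

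**Step 1: can the arm figure be reproduced from the total?** Expected arm n = N × 1/2 = 25 × 1/2 = 12.5. The stated figure is 25, so it is not reproduced.

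**Step 2: can the total be reproduced from the arm figure?** N = arm n ÷ 1/2 = 25 × 2 = 50. The stated total is 25, so it is not reproduced either.

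**Step 3: could chance imbalance explain it?** Section 6.3 mentions a random number generator and states no blocking. Assuming simple randomisation, the probability that all 25 go to coaching is 0.5^25 = 3.0 × 10⁻⁸, and that outcome would leave no control arm. The same assumption shows that 12.5 is an expectation and not a guaranteed split:

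- P(12/13 split) = 2 × C(25,12) / 2^25 = 2 × 5,200,300 / 33,554,432 = 0.31
- P(coached arm between 10 and 15) = 0.77
- P(coached arm between 8 and 17) = 0.96

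**Step 4: could an allowance for dropout explain it?** Inflating 12.5 to 25 requires 12.5 / (1 − d) = 25, so d = 0.50. No dropout rate is stated, and enrolment would then be 50, not 25.

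**Step 5: size of the difference.** Coached participants: 25 / 12.5 = 2. Total enrolment: 50 / 25 = 2. In the counts and proportions the protocol plans to report, one coached participant is worth 1/25 = 4 percentage points at n = 25, against 1/13 = 7.7 or 1/12 = 8.3 points at n = 13 or 12.

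**The case against.** The strongest reply is that n=25 is simply the study total, placed beside a name that the intervention shares with the study. On that reading 25 is right and only its position is wrong. This is possible and cannot be excluded from the text, so it would be too much to say that the two figures can never be reconciled. It does not rescue Section 6.1.1 as written, where the number sits in a description of the coached intervention.

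The replacement rule in Section 7.2, for people randomised who do not receive the intervention, does not help. It gives no number and does not turn 12.5 into 25. The flow diagram is not in the text available to me. It might show the intended arm sizes, but it could not remove the conflict between the written sections.

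It is also fair to say that the consequences are modest. The protocol disclaims a power calculation (Section 9.2) and inferential analysis (Section 9.3), and limits itself to descriptive statistics (Section 9.4.1). Recruitment and retention can be described for the whole study, whatever the coached-arm size.

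Some stronger readings are tempting but not supported:

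- **That 50 was the real target.** A reader might infer this because groups of five divide evenly into 25 (25/5 = 5) but not into 12 or 13 (2.4 or 2.6). That is weak evidence. The only total the documents state is 25; 50 is an inference.
- **That a specific monthly coaching load follows from each arm size.** Multiplying the weekly sessions by 25 would require everyone to be coached in the same month. The study runs 24 months with 6 months per participant (Section 1.1), and no passage says participants start together. Only the roughly twofold ratio survives, for a given pattern of accrual and attendance.
- **That the conflict turns on whether 25 counts people consented or people randomised.** The protocol does not define enrolment precisely, but that is a separate missing detail and does not bear on whether 25 is a total or an arm size.

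**Conclusion.** The inconsistency is real and should be corrected. Read as an arm size, the n=25 in Section 6.1.1 contradicts the synopsis total of 25 under 1:1 allocation: the coached arm is either 25 or 12.5 expected, and the total is either 25 or about 50. If n=25 is a misplaced study total, its placement is still wrong. The documents do not show which was intended.

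The 12.5 rests on 25 being the number randomised and on the stated 1:1 ratio. The realised split may differ, since no blocking is described. The effect is confined to planned enrolment and to the number of coached participants on whom acceptability, fidelity and coach capacity are described. A reader might go on to infer that the trial's conclusions or its power are compromised. The documents do not support that, because no power claim, success threshold or inferential result is planned.

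**What to change.** State one total number randomised and the expected number per arm (Section 9.2, which now gives no figure, is a natural place), and make Sections 1.1 and 6.1.1 agree with it.

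- If 25 in total stands, replace n=25 in Section 6.1.1 with *about 12-13 expected*.
- If 25 per arm was intended, correct the synopsis total to about 50.

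The first option costs wording only and needs no extra participants, but the stated coached-arm size falls to about half of what Section 6.1.1 now says. The second raises the stated total by about 25 people (50 − 25) at a single site. Since Section 9.2 ties the size to expected recruitment, the sponsor would need to confirm that this number is achievable.
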